11.1 Evaluation and Reporting of Adverse Events

All AEs (i.e., a new event or an exacerbation of a pre-existing condition) that occur from the baseline visit to the end of the pilot study and are related to the study procedures will be recorded as an AE in the study database. Adverse events that occur prior to the baseline visit will be documented as medical history. The Investigator will follow all AEs until the AE

resolves, or until the Investigator determines the event is chronic or clinically stable. If an AE remains unresolved at the conclusion of the study, the Investigator will make a clinical assessment to determine whether continued follow-up of the AE is warranted.

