5.2 Potential Risks and Benefits Associated with this Study

5.2.1 Potential Risks

Risks associated with study participation are minimal and may include fatigue and/or frustration associated with cognitive screening at baseline and participating in an online educational program. Questionnaires on mood and lifestyle risk may increase negative affect. In order to mitigate these risks, participants will be reminded they can skip questions or take breaks. If a participant mentions negative emotions, the study coordinator will alert [name], co-PI and clinical psychologist, who will attempt to contact the participant within 48 hours to suggest mental health resources.

There may be limits in protecting confidentiality during facilitated group discussions and focus groups. Participants will be reminded to keep group discussions confidential but this cannot be guaranteed.

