7.0 STUDY PROCEDURES

7.1 Study Visits

The schedule of study visits and procedures to be performed at each visit are outlined below and summarized in the Schedule of Events table (Appendix 1). A detailed description of study procedures is located in Section 8.0. and a detailed description of study instruments is located in Section 9.0

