7.2.3 Program Elements

Participants will be provided access to HALT-AD where they will participate for approximately 1-2 hours a month for 3 months, from home, with their own devices and at their own time. Information within the courses will contain scientific evidence, explanation of principles and mechanisms that underlie positive effects, specific recommendations (e.g. a healthy recipe to make at home), suggestions to improve behavior in everyday life and typical barriers and tips to circumvent them. Participants will also be able to revisit course material as often as they would like. Additional program elements will also include interactive activities, quizzes and a resource library.

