11.0 ADVERSE EVENTS

An adverse event (AE) is any untoward medical occurrence in a participant that occurs from the time of the baseline visit and up to 30 days after study participation has ended. For the purposes of reporting on the this study, an AE is defined as any unfavourable or unintended sign, symptom, or disease **associated with study participation** that is both non-serious and either temporally or causally related to study procedures. Pre-existing conditions, which increase in frequency or severity or worsen in nature during, or as a consequence of, a study procedure, may also be considered an AE if it meets the definition of being both non-serious and related to a study procedure. Adverse events that occur prior to the baseline visit will be documented as medical history.

An AE **does not** include:

- Medical or surgical procedures (e.g., surgery, endoscopy, tooth extraction, transfusion). The condition that leads to the procedure is the AE.
- Situations where an untoward medical occurrence has not occurred (e.g., hospitalization for elective surgery, social and/or convenience admissions).
- Worsening of symptoms associated with an associated co-morbid condition and not related to a study procedure.

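### Adverse event recording turns on an undefined term, ‘study procedures’, and no described contact asks about events, so harms from following the program’s advice can go unrecorded

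*Combined protocol and SAP*

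**What the plan says.** **Recording rule.** Section 11.1 enters in the database those events, from baseline to the end of the pilot, that "are related to the study procedures will be recorded as an AE in the study database".

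**Definition.** Section 11.0 opens its reporting definition with "For the purposes of reporting on the this study, an AE is defined as any unfavourable or unintended sign, symptom, or disease". It then requires the event to be associated with study participation and adds "that is both non-serious and either temporally or causally related to study procedures". Worsening of a pre-existing condition during, or as a consequence of, a study procedure may count. The list of what is not an adverse event includes "Worsening of symptoms associated with an associated co-morbid condition and not related to a study procedure". The window in Section 11.0 runs "from the time of the baseline visit and up to 30 days after study participation has ended".

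**What a study procedure is.** Section 7.1 says that visit procedures are outlined in the text that follows it and summarized in Appendix 1, and adds "A detailed description of study procedures is located in Section 8.0".

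**What the program asks of people.** Section 7.2.3 says the courses contain "specific recommendations (e.g. a healthy recipe to make at home), suggestions to improve behavior in everyday life". Participants also set goals from their risk profile (7.2.3.2) and join discussion groups meant to promote behavioral change (7.3). The pilot courses include diet, and sleep or physical activity (7.2.1).

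**Contacts.** Section 7.1.4 has a coordinator checking in by telephone or email, with no stated frequency. Discussion groups meet about every three weeks (7.3), and Month 4 has a set of surveys (7.1.5). Section 11.2 refers to an Adverse Event CRF.

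**The concern.** The program works by persuading people to change what they do at home. If it causes harm, one plausible route is through that change rather than through a questionnaire or a telephone screen. An event on that route passes two filters before it reaches the database. Someone must mention it unprompted in a fully remote study, and an investigator must then judge it related to *study procedures*, a term that can be read narrowly or broadly.

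Participants are aged 50 to 85. Appendix 4 collects history of diabetes, treated blood pressure, stroke and heart surgery, and no listed exclusion criterion names any of these. The knowledge survey in Appendix 2 has items on exercise, including one on symptoms during exercise, so activity advice is a realistic part of the content.

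The pilot is meant to inform changes to the program before full launch. At stake is whether a low or zero count of adverse events could carry any weight in that revision.

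**Working it through.** The plan states no adverse event rate, power or alpha, so there is no figure of its own to reproduce. The check is mainly textual.

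**Step 1. Does *study procedures* cover acting on program advice at home?**

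| Place | What it points to |
|---|---|
| Section 7.0 (heading: Study Procedures) | Includes the program, goal setting and the discussion groups |
| Appendix 1, procedures column | Lists goal setting and discussion groups; has no row for the courses |
| Section 8.0 (procedure descriptions) | Sociodemographics, history, height/weight/BMI, hearing and vision only |
| Section 11.0, definition | Requires association with study participation and a temporal or causal relation to study procedures |
| Section 11.0, co-morbidity exclusion | Study procedure only |
| Section 11.1, recording rule | Study procedures only |
| Section 11.2, *Not Related* and *Unlikely Related* | Study procedures |
| Section 11.2, *Probably* and *Definitely Related* | Study participation |

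A broad reading is available from Section 7.0 and Appendix 1, and a narrow one from Section 8.0. No entry says whether a diet or activity change made at home because of a course is within the term. Two investigators could classify the same event differently, and both could cite the protocol.

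**Step 2. Does any contact ask?**

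- Coordinator check-ins (7.1.4): check-in, reminders, answers to questions; no health question is described.
- Discussion groups (7.3): course content and behavior change; no adverse event question is described.
- Month 4 (7.1.5): user experience, Net Promoter Score, two acceptability surveys, knowledge, self-efficacy, lifestyle risk, goals; no adverse event item.
- Appendix 1: no adverse event row in any column.
- Negative emotions (5.2.1): acted on if a participant mentions them.
- Adverse Event CRF (11.2): exists, but no section says how an event comes to be entered on it.

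This result does not depend on how Step 1 is resolved.

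**Step 3. What would a count of zero mean?** This is an illustration. N = 20 is from Section 6.0. The true risk per participant, p, and the fraction of affected participants captured, c, are assumptions. It treats participants as independent and all 20 as followed.

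Chance of at least one recorded event = 1 − (1 − p·c)^20:

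| p | c = 1 | c = 0.75 | c = 0.5 | c = 0.25 |
|---|---|---|---|---|
| 5% | 64.2% | 53.4% | 39.7% | 22.2% |
| 10% | 87.8% | 79.0% | 64.2% | 39.7% |
| 20% | 98.8% | 96.1% | 87.8% | 64.2% |

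One-sided 95% upper limit after 0 of 20 = 1 − 0.05^(1/20) = 13.9% for recorded events. Dividing by c gives the matching limit for true risk: 18.5% at c = 0.75, 27.8% at c = 0.5 and 55.6% at c = 0.25.

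**Step 4. Is Section 11 consistent with itself?** Three pairs do not agree:

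- Section 11.0 confines the definition to non-serious events, while 11.2 records seriousness. No separate route for serious events is described.
- Section 11.0 runs to 30 days after participation ends, while 11.1 runs to the end of the pilot study.
- Section 11.1 records related events only, while the scale in 11.2 includes a *Not Related* grade.

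**The case against.** A reader might infer that every harm from program advice falls outside the recording rule. The documents do not support that. An event has only to be related to a procedure; it need not be one. Section 11.0 accepts a temporal relation and allows worsening as a consequence of a procedure. Goal setting and discussion groups are listed as procedures in Appendix 1, so an injury while pursuing a program goal can be read as related. The co-morbidity exclusion removes only unrelated worsening. All of this stands, and it reduces the first half of the point to an ambiguity.

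A reader might also infer that the pilot decides whether the program launches. The Background & Rationale entry in the synopsis and Sections 1.2 and 7.1.6 say it informs improvements and a second prototype. There is no go/no-go rule and no safety aim.

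Nor is Section 5.2.1 shown to be deficient. Its list, such as "fatigue and/or frustration associated with cognitive screening at baseline and participating in an online educational program", is introduced as what the risks may include, so it is not closed. Adding to it would be a preference.

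Appendix 1 is not exhaustive: it also omits the coordinator check-ins and the medication record. A missing row alone is therefore weak evidence. Contacts do exist, and the study is described as minimal risk, with about one to two hours of use a month. Even so, no section says that any contact asks about adverse events, and that part of the point is unanswered.

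**Conclusion.** The point holds in a limited form. The relatedness term that controls recording does not settle whether home behavior prompted by the program counts. Separately, and on either reading, no enquiry about adverse events is described. Harms from following the program can go unrecorded; the text does not make that certain.

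The size of any loss cannot be estimated from the documents, because neither an event rate nor a capture fraction is given. The figures above show only direction: with 20 participants, zero recorded events is compatible with a risk of up to 13.9% under full capture, and with more under partial capture. A statement that no harms occurred would have little support.

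No primary or secondary outcome or analysis in Section 12.1 is affected. This is a cheap improvement to harm capture. The three inconsistencies in Section 11 are plain on the text and need no assumption.

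**What to change.** 1. In Sections 11.0 to 11.2, including the co-morbidity exclusion and the relatedness table, use one term throughout. It should expressly cover study procedures and acting on HALT-AD course content, goals or discussion-group advice.
2. Add one standard question on new or worsened health problems to the existing coordinator check-ins and to the Month 4 REDCap survey, and add an adverse event row to Appendix 1.
3. Reconcile three pairs of passages: the non-serious definition (11.0) with the recording of seriousness (11.2); the 30-day window (11.0) with the end of the pilot study (11.1); and related-only recording (11.1) with the *Not Related* grade (11.2). Step 1 alone would leave serious events outside the definition.

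The cost is protocol wording, one question and one table row. The downside is a few more minor events to document. No clinical management rule is proposed.

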11.2 Assessment of Adverse Events

All AEs will be promptly documented on the Adverse Event CRF and assessed by the Investigator. Details of the event will include the dates of onset and resolution, severity, relationship to study procedures, seriousness, whether the event caused the participant to withdraw from the study, and outcome.

Severity: Severity will be graded and recorded according to the table below.

Severity	Definition
Mild	Awareness of event but easily tolerated
Moderate	Discomfort enough to cause interference with usual activity
Severe	Inability to carry out usual activity, incapacitating, requires medical intervention

Relationship: The relationship of the AE to study procedures will be determined by the Investigator, and assessed using the following definitions:

Relatedness	Description
Not Related	There is no evidence of a causal relationship and a causal relationship cannot be reasonably attributed to the study procedures. The event is clearly due to extraneous causes.
Unlikely Related	A poor temporal relationship exists between the event onset and study procedures. The event could easily be explained by the participant’s clinical state, intercurrent illness, or concomitant therapies.
Possibly Related	A relationship cannot be ruled out with certainty and the event may be related. There is some evidence to suggest a causal relationship but the influence of other factors may have contributed to the event, such as the participant’s clinical condition or concomitant treatment.
Probably Related	The event is likely related to study participation. There is evidence to suggest a causal relationship, such as reasonable temporal sequence from procedure. The influence of other factors is unlikely.
Definitely Related	The event is clearly related to study participation. There is clear evidence to suggest a causal relationship. The influence of other factors can be ruled out.

These criteria, in addition to good clinical judgment, should be used as a guide for determining the causal assessment.

12.0 STATISTICAL CONSIDERATIONS

12.1 Analysis Plan

Descriptive statistics will be provided for each timepoint on HALT-AD measures and change scores will be computed where applicable. Change = (4 months score - baseline score). Continuous data will be presented with mean, standard deviations, median, minimum and maximum and 95% confidence intervals. Categorical data will be presented as proportions and percentages. We will examine the proportion of participants reaching a defined threshold on usability measures. Changes in continuous outcome measures between baseline and post-intervention will be analyzed by repeated measures t-test.

Furthermore, the continuous measures collected directly from the program will be analyzed to evaluate program use during the 3-month period. User engagement as measured by the average total amount of time (in minutes) spent on all courses combined and the percentage of participants who completed all courses, overall and by age, gender and educational level will be tracked.

The post-pilot interviews/focus groups will collect more detailed feedback on the experience with the program and these will be guided by the results obtained on the usability and functionality questionnaires. Qualitative analyses (content analysis) will be used for responses to open-ended questions (e.g. suggestions for improvements of the web platform) obtained during focus groups. Answers to open-ended questions will be first transcribed verbatim in Word, then the text will be imported into MAXQDA. Thematic analysis will be conducted in MAXQDA to identify common themes arising from the focus group discussions. Themes will be defined and described in a Table format. Saturation will be reached and analysis will be considered complete when no new themes are identified.

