	
 • The percentage of participants who completed all courses 
Secondary Outcome Measures:
 
 1. Preliminary evidence on the effectiveness of the program in changing knowledge, self-efficacy, and dementia-related lifestyle risk factors will be evaluated by: 
 • Change from baseline in knowledge on the HALT-AD knowledge assessment survey at 4 months • Change from baseline in self-efficacy on the New General Self-Efficacy Scale at 4 months • Change from baseline in lifestyle risk on the HALT-AD Lifestyle Risk Assessment Survey at 4 months 
Exploratory Outcome Measures:
 
 1. Users’ acceptability of the HALT-AD program content will be determined by: 
 • HALT-AD Course Acceptability Survey • Focus group discussion 2. Users’ acceptability and satisfaction with the facilitated support discussion groups will be determined by: 
 • Facilitated support discussion group Acceptability Survey • Focus group discussion 3. The usability of the online platform will be evaluated by: 
 • HALT-AD User Experience Survey • Net Promotor Score Survey

Statistical Plan
	
Descriptive statistics will be used for quantitative data. Change scores will be computed where applicable. Change = (4 months score - baseline score). Continuous data will be presented with mean, standard deviations, median, minimum and maximum and 95% confidence intervals. Categorical data will be presented as proportions and percentages. Changes in continuous outcome measures between baseline and post-intervention will be analyzed by repeated measures t-test.
 
Qualitative data generated from focus groups, logs, and open-ended survey questions will be thematically analyzed using inductive qualitative coding.
 
Sample Size and Power
 
Given that this pilot study is being conducted to contribute to the development of the HALT-AD program, we did not power to detect an

	intervention effect size over time. The sample size for the pilot was estimated based on prior experience in the development of similar programs.
--	---

TABLE OF CONTENTS

LIST OF ABBREVIATIONS:	9
1.0 INTRODUCTION	10
1.1 BACKGROUND	10
1.2 RATIONALE	10
2.0 STUDY DESIGN	11
3.0 STUDY GOAL AND AIMS	11
3.1 OVERALL GOAL	11
3.2 AIMS	11
4.0 OUTCOME MEASURES	12

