6.0 PARTICIPANT SELECTION

A total of 20 participants will be enrolled at UCSD with 50% (n=10) completing the English version of HALT-AD and 50% (n=10) completing the Spanish version. We are aiming to recruit

50% women and to enroll a diverse participant sample across varied age ranges within both language groups.

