7.1.6 Post-Pilot Focus Groups

Following completion of the 3-month HALT-AD program, participants may be invited to participate in an end of study remote focus group(s) to further evaluate user-experience and satisfaction with HALT-AD. This will allow the study team to address in more detail the components that have been surveyed in the questionnaires on usability and acceptability: (e.g. level of difficulty and interest in the content, strengths and weaknesses, confidence in the content, applicability and impact in everyday life, clarifications, quality of design, animation and visual effects, effort needed, motivation for behavioral change). Participant feedback and responses will be used to make any necessary changes to the web-based HALT-AD program prior to launch of the full program. Total time to participate in the focus group is approximately 2 hours (1 hour to discuss web-based platform and 1 hour to discuss facilitated discussion groups).

Focus groups will be conducted remotely over video-call in smaller groups of approximately 5-10 other participants. Participants will need access to a computer, tablet or mobile device capable of making video-calls. The focus group discussions will be audio-recorded for transcription. All identifiable information will be removed from the transcripts and replaced by unique coded Participant ID number. Recordings will be destroyed once the focus group discussion has been transcribed.

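### The saturation rule in section 12.1 is met once the available transcripts are coded, so meeting it does not itself show saturation

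*Combined protocol and SAP*

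**What the plan says.** The completion rule is in section 12.1 (Analysis Plan): "Saturation will be reached and analysis will be considered complete when no new themes are identified". The sentences before it set the aim and the material: "Thematic analysis will be conducted in MAXQDA to identify common themes arising from the focus group discussions".

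The synopsis (Statistical Plan) casts the net wider: "Qualitative data generated from focus groups, logs, and open-ended survey questions will be thematically analyzed using inductive qualitative coding". Section 12.1 also mentions interviews once: "The post-pilot interviews/focus groups will collect more detailed feedback on the experience with the program". Neither section 7.1.6 nor the Schedule of Events describes any interviews.

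The number of people is set in section 6.0: "A total of 20 participants will be enrolled at UCSD with 50% (n=10) completing the English version of HALT-AD", with the other 10 completing the Spanish version. Section 7.1.6 says only that participants may be asked to join one or more groups, and gives their size: "Focus groups will be conducted remotely over video-call in smaller groups of approximately 5-10 other participants". It does not state how many groups there will be, a minimum attendance, or whether groups are formed by language. Section 12.2 bases the sample size on prior experience and does not link it to saturation.

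**The concern.** Saturation is a statement about the data: further material has stopped yielding anything new. To support it, one normally either keeps collecting until nothing new appears, or shows that the later part of a fixed collection added nothing to the earlier part. Section 12.1 does neither. Its rule decides when the analysis ends, while the amount of material is decided by enrolment and attendance. Once the last transcript has been fully coded there is nowhere left for a new theme to come from, and the condition holds. The wording leaves no outcome in which saturation is not reached.

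At stake is how the qualitative results are read. Under section 7.1.6, focus-group feedback drives changes to the program before full launch. Focus groups are also a named measure for two exploratory outcomes in section 4.3: acceptability of the content and of the facilitated discussion groups. A report that says saturation was reached invites readers to trust the theme list more than the design justifies.

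**Working it through.** **The plan's own figure.** Section 6.0: 20 × 50% = 10 per language, which checks. The total of 20 cannot be reproduced, because section 12.2 gives no formula or inputs. The plan states no number of focus groups.

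**Number of groups** = attendees ÷ group size, with sizes of 5 to 10 from section 7.1.6.

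- Languages pooled, all 20 attending: 20/10 = 2 to 20/5 = 4 groups.
- Split by language, all 10 attending: 10/10 = 1 to 10/5 = 2 groups per language.
- Split, with 5 to 9 attending in a language: only one group of at least 5 is possible.
- If the size is read literally as 5 to 10 people besides the participant (6 to 11 in all), 10 people form one full group.

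**What the groups can show.** With one group there is no later group in which to look for new themes. With two there is a single comparison. With four there are three successive comparisons.

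**How likely a theme is to be missed (illustration).** The documents give no theme prevalences, so a range is assumed. If each person voices a theme independently with probability p, the chance that n people never voice it is (1 − p)^n.

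| p | n = 10 | n = 20 |
|---|---|---|
| 0.05 | 0.95^10 = 60% | 0.95^20 = 36% |
| 0.10 | 0.90^10 = 35% | 0.90^20 = 12% |
| 0.20 | 0.80^10 = 11% | 0.80^20 = 1% |
| 0.30 | 0.70^10 = 3% | 0.70^20 = 0.1% |

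**How strong one comparison is (illustration).** Take two groups of 5 and 10 themes, each with the same p. Let q = (1 − p)^5 be the chance that one group misses a given theme.

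- The second group adds nothing new with probability [1 − q(1 − q)]^10.
- The first group has already covered all 10 themes with probability (1 − q)^10.
- Given nothing new in the second group, at least one theme is still unheard with probability 1 − (1 − q)^10 / [1 − q(1 − q)]^10.

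At p = 0.20, q = 0.328, and this is 1 − 0.019/0.083, about 77%. At p = 0.30, q = 0.168, and it is 1 − 0.159/0.222, about 28%. A second group that adds nothing is some evidence, but weak unless the themes are common.

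**The case against.** The best defence reads the sentence as a rule for when coding stops: coders go over the transcripts until another pass yields nothing. On that reading it makes no claim that enough people were sampled, and it is not met merely because the transcripts run out, since recoding can still find themes. This is a fair reading of the second half of the sentence. It does not account for the first half, which uses the word saturation and says it will be reached. A stable codebook for a fixed set of transcripts is a different property.

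Four further points limit what may be concluded, and they stand.

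- **Language split.** A reader might infer that there will be at most two groups per language. With two language versions this is natural, but the plan does not say so and proposes no theme analysis by language. Pooled, there could be two to four groups, and the word approximately does not rule out an extra small one.
- **Impossibility.** A reader might infer that the design cannot show saturation at all. That is too absolute, because two or more groups allow a weak check.
- **Completeness.** A reader might infer that the plan promises a full list of the prototype's problems. Its stated aim is common themes, and at p = 0.30 the chance of missing one is 3% or less.
- **Other sources.** The synopsis adds logs and open-ended survey answers. The Course Acceptability Survey sends several open questions (items 2, 5, 8 and 11) to people who gave less favourable ratings. These widen the material, but it remains finite and comes from the same 20 people, so the rule is still met when coding ends.

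No primary or secondary outcome and no decision threshold uses saturation.

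**Conclusion.** The point holds as a minor one. Section 12.1 states that saturation will be reached, which a fixed pool of 20 and an unstated number of groups do not guarantee, and its rule has no failing outcome. The conclusion rests on the text alone: no passage adds groups, tracks new themes by group, or allows for saturation not being reached.

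The practical effect is confined to exploratory acceptability outcomes and prototype redesign. Themes voiced by 30% or more of users would probably appear even among 10 people. Less common ones may not: at 5% to 20% prevalence the chance of missing a theme is 60% to 11% with 10 people and 36% to 1% with 20. These figures assume the prevalences, full attendance, and that people speak independently. In a group discussion people respond to each other, so they indicate scale only.

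**What to change.** In section 12.1, replace the saturation sentence with:

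> All transcripts will be coded in full; the number of new themes contributed by each successive focus group will be tabulated (within language if groups are held by language); saturation will be reported as not shown if the last group still adds themes, and as not assessable if only one group was held.

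It would help if section 7.1.6 also stated how many groups are planned and whether they are formed by language, since that determines what the table can show.

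The cost is one sentence and one small table, with no added participants or procedures. The qualitative claim becomes more modest: where only one group is held, the report will have to say that saturation could not be assessed.
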